## 9.2.6 No of days free from oxygen

Number of days free from oxygen support will be compared between the treatment arms using the negative binomial regression with time in ICU as the offset. Number of days will be calculated as the number of days free from oxygen support reported on the 7-point ordinal scale eCRF.

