3.7. Table of endpoints/outcomes

Objectives	Outcome Measures	Timepoint(s)
Primary Objective Participant clinical status (on a 7- point ordinal scale) In accordance with WHO recommendations the primary endpoint will be determined by a pilot trial of the first 100 participants.	 7-point ordinal scale: Not hospitalised, no limitations on activities Not hospitalised, limitation on activities; Hospitalised, not requiring supplemental oxygen; Hospitalised, requiring supplemental oxygen; Hospitalised, on non-invasive ventilation or high flow oxygen devices; Hospitalised, on invasive mechanical ventilation or ECMO (Extracorporeal membrane oxygenation) Death. 	Up to day 29
Secondary Objectives	Outcome Measures	Timepoint(s)
Evaluate the clinical efficacy of Brensocatib relative to standard care in adult patients hospitalised with COVID-19	Clinical Severity Time to an improvement of one category from admission using 7-point ordinal scale. Participant clinical status on 7-point ordinal scale Mean change in the 7-point ordinal scale	Daily whilst hospitalised Days 3, 5, 8, 11, 15 and 29. Baseline to days 3, 5, 8, 11, 15 and 29.
	National Early Warning Score (NEWS): Time to discharge or to a NEWS of ≤ 2 and maintained for 24 hours, whichever occurs first. Change from baseline Oxygenation:	Daily whilst hospitalised Days 8, 15, 29
	Oxygen free days Incidence and duration of new oxygen use during the trial	1-29 days 0-29 days
	Mechanical Ventilation: Ventilator free days	1-29 days

	Incidence and duration of new mechanical ventilation use during the trial.	1-29 days
	Hospitalisation:	
	Duration of hospitalisation (days).	Date of admission and discharge
	Mortality:	
	28-day mortality	Date of death
Evaluate the safety of the	Cumulative incidence of SAEs	1-29 days
intervention through 28 days of follow-up as compared to the control arm	Discontinuation or temporary suspension of treatment	1-29 days
	Changes in white cell count, haemoglobin, platelets, creatinine, total bilirubin, ALT, and AST over time (hospitalised participants only)	Days 0/1, 3, 5, 8, 11, 15, 29
	Adverse events of special interest- hyperkeratosis, infections and dental complications	1-29 days
	dental complications	
Exploratory Objectives	Outcome Measures	Timepoint(s)
Exploratory Objectives Evaluate the virologic efficacy of Brensocatib	·	Timepoint(s) Day 15 and day 29

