#### 7.3.2 Subgroups

The primary endpoint will be analysed for the following participant subgroups:

1. Age (years): (a) <65 years and (b)  $\ge 65$ 

- 2. Sex at birth: (a) Male and (b) Female
- 3. Symptom duration (days): (a) <10 and (b)  $\ge 10$
- 4. Baseline 7-point ordinal scale: (a) 3, (b) 4 and (c) 5
- 5. Co-enrolment into RECOVERY: (a) Yes and (b) No
- 6. Co-treatment with dexamethasone: (a) Yes and (b) No (if a meaningful number if patients did not receive dexamethasone)

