#### 9.2.9 No of days free from ventilation

Number of days free from ventilation will be compared between the treatment arms using negative binomial regression with time in ICU as the offset.

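### Oxygen-free and ventilation-free days are compared by negative binomial regression with no robust variance named; if all of days 1 to 29 are scored, the intervals on these two secondary endpoints come out too wide

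*SAP*

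**What the plan says.** The endpoint table in Protocol 3.7 lists oxygen-free days and "Ventilator free days" as secondary outcomes, each over days 1 to 29, so neither count can exceed 28 or 29.

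For the first, SAP 9.2.6 states: "Number of days free from oxygen support will be compared between the treatment arms using the negative binomial regression". The same sentence adds an offset: "using the negative binomial regression with time in ICU as the offset". It defines the count this way: "Number of days will be calculated as the number of days free from oxygen support reported on the 7-point ordinal scale eCRF". SAP 9.2.9 reads: "Number of days free from ventilation will be compared between the treatment arms using negative binomial regression with time in ICU as the offset". SAP 7.7 adds centre as a random effect for secondary outcomes.

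Neither section names a robust variance, a bounded-count model or a rank method. Neither says how a death scores, or whether days between telephone contacts after discharge are filled in. No mean, variance or expected distribution is given for either count.

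**The concern.** A negative binomial model has no upper limit and takes the variance to be the mean plus a dispersion parameter times the mean squared. Free-day counts are the reverse of what that model expects. They are bounded above and mostly high, with a tail of low values from patients who die or need long support. Maximum likelihood accommodates the low tail by raising the dispersion, and the model-based standard error rises with it, although the sampling error of the mean does not.

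At stake are the confidence intervals and p-values of two named secondary efficacy endpoints. A real benefit on oxygen or ventilator dependence could be reported as inconclusive.

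**Working it through.** **Inputs.** From the documents: 400 patients allocated 1:1 (200 per arm), two-sided 5% level, day 1 to 29 window, negative binomial regression. The documents give no figure for these endpoints to reproduce, because the sample size calculation covers only the primary endpoint. All distributions below are assumptions. Steps 1 to 3 leave out the ICU offset to isolate the variance question.

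**Step 1. Formulas.** With n per arm, mean m and variance v in both arms:

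- true SE of the log ratio of means ≈ √[2v/(n m²)]
- model-based SE = √[2(1/m + α)/n]

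The two agree only if α = (v − m)/m².

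**Step 2. Three counts capped at 28, n = 200.** The fitted α is the median from simulation.

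| Assumed distribution | m | v | α needed | α fitted | True SE | Model SE | Ratio |
|---|---|---|---|---|---|---|---|
| 90% at 28, 10% at 0 | 25.2 | 70.6 | 0.071 | 0.313 | 0.033 | 0.059 | 1.78 |
| 85% at 28, 15% at 4 | 24.4 | 73.4 | 0.082 | 0.191 | 0.035 | 0.048 | 1.37 |
| Uniform on 8 to 28 | 18.0 | 36.7 | 0.058 | 0.062 | 0.034 | 0.034 | 1.02 |

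First row in full: α needed = (70.56 − 25.2)/25.2² = 0.071. True SE = √[2 × 70.56/(200 × 635.04)] = 0.0333. Model SE = √[2 × (0.0397 + 0.313)/200] = 0.0594. Direct simulation of the three rows gave ratios of 1.77, 1.38 and 1.02, with type I error 0.0%, 0.9% and 4.9%. Mass at or near zero does the damage.

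**Step 3. Simulations with every day scored, 200 per arm.** Paired power figures are model-based, then robust.

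| Assumptions | SE ratio | Type I error, model-based | Type I error, robust | Power |
|---|---|---|---|---|
| Oxygen: 20% never on oxygen; deaths 2/5/10%; effect 25% shorter use and 40% fewer deaths | 1.21/1.29/1.35 | 1.9/1.3/0.7% | – | 59/54/49% v 68/70/72% |
| Ventilation: 94/90/82% at cap; effect halved death and ventilation | 1.26/1.06/1.26 | 1.5/3.6/1.1% | – | 6/33/53% v 25/42/66% |
| 11 distributions; 10–97% at cap, 0–20% at zero; latent odds ratio 1.75 | 1.09–1.96 | 0.0–3.3% | 4.2–5.8% | oxygen 22–73% v 76–86%; ventilation 0.1–17% v 12–48% |
| 24 oxygen scenarios; median use 7 days, 10–40% never on oxygen, deaths 2–15% scored 0 or by days survived; effect as in row 1 | 1.25–1.79 | 0.1–1.4% | 3.9–7.1% | 21–74% v 52–92% (loss 13–52 points) |

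A further run with a 29-day cap gave ratios of 1.24–1.56, type I error 0.1–1.9%, and power 40–63% against 71–79%. In the 11-distribution run a rank test had power of 86–90% for oxygen and 15–52% for ventilation. The effect there was generated as an odds ratio, which favours rank methods.

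**Step 4. Only recorded days scored.** The schedules (Protocol Appendix 4, SAP 5.4) record the ordinal scale daily in hospital, but after discharge only at those of days 3, 5, 8, 11, 15 and 29 that remain. Counting only those records, with an assumed median stay of 7 days, 20% never on oxygen and deaths of 2/5/10%, leaves about 1% at the cap. The SE ratio is then 0.89/0.94/0.91 and type I error 7.0/6.2/8.0%. A second simulation of this reading gave ratios of 0.99–1.06.

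**Step 5. Offset kept as written.** The log of zero ICU time is undefined, so patients never in ICU drop out of the fit. With 15–30% assumed to enter ICU, about 50 to 120 of 400 remain. Model-based power is at most 4%, and robust power only 6–14%.

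**The case against.** The strongest objection is that Step 3 does not simulate the model in the SAP, which has an ICU-time offset and a centre random effect. That stands as a limit: the figures describe what remains once the offset is gone. A reader might infer that robust standard errors alone would rescue these endpoints, and Step 5 shows that they would not. Equally, deleting the offset alone would leave a poorly calibrated test if all days are scored.

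Second, a reader might infer that the intervals will certainly be too wide. The documents do not support that. The wording in SAP 9.2.6 can be read as counting recorded days only, and Step 4 then shows little error, or a slight one in the other direction.

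Third, a reader might infer that both counts pile up at the maximum. That is plausible mainly for ventilation-free days. The subgroup list in SAP 7.3.2 ("Baseline 7-point ordinal scale: (a) 3, (b) 4 and (c) 5") shows patients already on oxygen or respiratory support at baseline. They cannot reach the oxygen-free maximum, so that count is only skewed towards high values. The fault does not need exact pile-up: with 10% never on oxygen the ratio was still 1.31–1.69.

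Fourth, the size rests on assumed distributions. That is true, and it ranges from about 2% to about 100% excess width.

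**Conclusion.** The point holds conditionally. If all of days 1 to 29 are scored, and apart from the offset, the model-based standard error is about 1.1 to 2 times the true one, type I error is about 0 to 3%, and power is often 10 to 50 points below that with robust errors. With moderate spread and no counts near zero, the excess can be as little as 2%. Scoring deaths as zero makes it worse: ratios were 1.33–1.79 in the 24-scenario run. If only recorded days are scored, the standard error is about right or slightly too narrow.

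The primary analysis and the sample size are unaffected. Both endpoints are secondary and have no power statement. Where the intervals are too wide the error is conservative, so a reader should not infer a risk of false positive claims from that reading. The harm is missed or blurred benefit.

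**What to change.** In SAP 9.2.6 and 9.2.9, remove the ICU-time offset, and state how deaths and days after discharge enter the count. Then choose one of two analyses:

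- Keep the ratio of means, with heteroscedasticity-robust standard errors, confidence intervals and p-values. Do not cluster these on the roughly 15 centres (Protocol 5) without a small-sample correction: with assumed unequal site sizes, a clustered sandwich gave type I error of 7–10%.
- Analyse the day counts with the proportional-odds mixed model already specified in SAP 9.1.

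Either is about correctly calibrated under both definitions of the count. The cost is a few sentences and a changed regression command, with no new data. The downsides are small: the ordinal model replaces a ratio of means with an odds ratio, and robust errors need care alongside the centre random effect of SAP 7.7.

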#### 5.2.1 Inclusion criteria

- Male or female
- $\geq 16$  years of age
- SARS-CoV-2 infection (clinically suspected+ or laboratory confirmed\*).
- Admitted to hospital as in-patient less than 96 hours prior to randomisation^
- Illness of any duration, and at least one of the following:
  - Radiographic infiltrates by imaging (e.g. chest x-ray, computed tomography (CT) scan)

OR

- Evidence of rales/crackles on physical examination OR
- Peripheral capillary oxygen saturation (SpO2) ≤94% on room air prior to randomization

OR

Requiring supplemental oxygen.
 OR

- Lymphocyte count <1 x 109 cells per litre (L)
- Participant (or legally authorized representative) provides written informed consent
- Able to take oral medication
- Participant (or legally authorised representative) understands and agrees to comply with planned trial procedures.

\*Laboratory-confirmed: SARS-CoV-2 infection as determined by polymerase chain reaction (PCR), or other commercial or public health assay in any specimen < 96 hours prior to randomization.

+Clinically suspected: in general, SARS-CoV-2 infection should be suspected when a patient presents with (i) typical symptoms (e.g. influenza-like illness with fever and muscle pain, or respiratory illness with cough and shortness of breath); and (ii) compatible chest X-ray SAP version 2 STOP COVID-19

05-04-2021

Page 10 of 46

findings (consolidation or ground-glass shadowing); and (iii) alternative causes have been considered unlikely or excluded (e.g. heart failure, influenza). However, the diagnosis remains a clinical one based on the opinion of the managing doctor

^Where a patient has been admitted to hospital for a non COVID-19 reason and develops COVID-19 symptoms whilst an in-patient, randomisation may occur up to 96 hours from onset of symptoms.

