## 7.4 Missing Data

(ICH E3; 9.7.1, 11.4.2.2. ICH E9;5.3. EMA Guideline on Missing Data in Confirmatory Clinical Trials)

All reasonable efforts will be taken to minimise loss to follow-up, which is expected to be minimal as data collection for primary and secondary outcomes using trial-specific eCRFs is combined with linkage to routine clinical data on study outcomes. The number and percentage of participants with follow-up information at day 29 after the randomisation will be reported. For all participants who were discharged and alive but have missing clinical status, a clinical status scale of 2 (Not hospitalised, limitation on activities) will be applied.

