## 9.2.7 Duration of new oxygen used

Duration of new oxygen used will be calculated and will be compared between the treatment arms using the negative binomial regression with time in ICU as the offset.

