#### 9.2.11 Duration of hospital stay - days

Duration of hospitalization will be calculated only for participants who are discharged alive on or prior to Day 29 and will be compared between the treatment arms using negative binomial regression.

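### Four oxygen and ventilation secondary outcomes use time in ICU as the offset, which is not the time at risk: the ratios become days per ICU day and, with a log offset, participants never in ICU drop out

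*SAP*

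**What the plan says.** Four sections of the SAP specify the same offset:

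- 9.2.6, oxygen-free days: "compared between the treatment arms using the negative binomial regression with time in ICU as the offset". The days are counted from the 7-point scale form.
- 9.2.7, duration of new oxygen: "using the negative binomial regression with time in ICU as the offset".
- 9.2.9, ventilation-free days: "using negative binomial regression with time in ICU as the offset".
- 9.2.10, duration of new ventilation: the same wording as 9.2.9.

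Section 9.2.11 treats another count of days, hospital stay, differently. It "will be compared between the treatment arms using negative binomial regression" and names no offset.

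The protocol's endpoint table (section 3.7) lists the oxygen outcomes as "Oxygen free days Incidence and duration of new oxygen use during the trial", with windows of days 1-29 for oxygen-free days and 0-29 for new oxygen. Both ventilation outcomes have a window of days 1-29.

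The entry criterion on setting is "Admitted to hospital as in-patient less than 96 hours prior to randomisation" (SAP 5.2.1; the protocol agrees in 6.1). ICU admission is not required. The planned subgroups include "Baseline 7-point ordinal scale: (a) 3, (b) 4 and (c) 5" (SAP 7.3.2), so patients without oxygen and patients on simple supplemental oxygen are expected.

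**The concern.** The offset in a count model should carry the time over which the counted days could accrue. Here that is the trial window. Oxygen-free and ventilation-free days accrue on the ward and at home as well as in ICU, and the 7-point scale has no ICU category.

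Three consequences follow.

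- **Participants lost.** With the usual log offset, zero ICU days gives log(0). The SAP has no rule for this, so participants never in ICU drop out and the comparison is conditioned on an event after randomisation. That departs from the full analysis population in SAP 7.2.1.
- **A different quantity.** The ratio compares days per ICU day, not days per participant over the window.
- **A denominator that treatment may change.** Protocol section 1 names a shorter ICU stay as a goal of COVID-19 therapy. Dividing by it can hide, create or reverse an effect on the outcome.

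Fewer days on oxygen or ventilation is part of the stated hypothesis (Protocol section 1, SAP 3.1), and SAP output Table 9 provides for effect estimates with 95% confidence intervals for these outcomes.

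**Working it through.** The documents give no expected value or power for these outcomes, so there is no planned figure to reproduce.

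**Inputs.** From the documents: 400 participants, 1:1, and a window to day 29. Assumed, because the documents give nothing: ICU share 5-40% (20% in the examples), mean control ICU stay 8 days, and mean oxygen outside ICU (ward oxygen) 4 days.

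**1. What the model estimates.** log E(Y) = log(ICU days) + b0 + b1 × arm. So exp(b1) is approximately (mean Y / mean ICU days) in the treated arm divided by the same quantity in control, among participants with ICU time. For one participant with 10 oxygen-free days:

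- per day of the window: 10/29 = 0.34
- per ICU day after 1 ICU day: 10/1 = 10.0
- per ICU day after 10 ICU days: 10/10 = 1.0

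**2. Participants lost from the two free-days analyses.**

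- ICU share 5%: 400 × 0.95 = 380 lost
- ICU share 20%: 400 × 0.80 = 320 lost, 80 analysed
- ICU share 40%: 400 × 0.60 = 240 lost

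**3. Reversal: treatment shortens ICU stay from 8 to 4 days, ward oxygen 4 days in both arms, 20% in ICU.**

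- Mean oxygen days in ICU participants: control 8 + 4 = 12; treated 4 + 4 = 8.
- All participants: control 0.8 × 4 + 0.2 × 12 = 5.6; treated 0.8 × 4 + 0.2 × 8 = 4.8. Ratio 4.8/5.6 = 0.86, a benefit.
- ICU offset: (8/4)/(12/8) = 2.0/1.5 = 1.33, an apparent harm.

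**4. Equal ICU use: stay 8 days in both arms, ward oxygen falls from 4 to 2 days.**

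- All participants: treated 0.8 × 2 + 0.2 × 10 = 3.6; 3.6/5.6 = 0.64.
- ICU offset: (10/8)/(12/8) = 0.83.

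The offset now cancels between arms, but the ratio describes ICU participants only and misses most of the effect.

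**5. Simulation check.** 200 per arm, ICU stay 1 + Poisson, ward oxygen Poisson, cap 29 days, dispersion 0.3, log ICU days as offset, median of 300 runs. The no-offset model uses all 400.

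| Scenario (20% in ICU) | n with offset | Duration ratio, ICU offset | Duration ratio, all | Free-days ratio, ICU offset | Free-days ratio, all |
|---|---|---|---|---|---|
| Stay 8 vs 8, no effect | 81 | 1.00 | 1.01 | 1.02 | 1.00 |
| Stay 8 to 7 | 80 | 1.06 | 0.96 | 1.22 | 1.01 |
| Stay 8 to 4 | 80 | 1.39 | 0.85 | 2.68 | 1.04 |
| Stay 8 vs 8, ward oxygen 4 to 2 | 79 | 0.82 | 0.64 | 1.12 | 1.09 |

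These agree with steps 3 and 4. The approximation in step 1 gives 1.33 where the fitted model gives 1.39, because participants with short stays pull the fitted ratio.

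**6. An effect created from nothing.** In a separate simulation, oxygen-free days were drawn with no treatment effect and independently of ICU days, at ICU shares of 10%, 20% and 30%. Mean ICU stay of 10 vs 8 days gave a ratio of about 1.27-1.28, and 10 vs 5 days about 2.13-2.14. With the 29-day window as exposure, the ratio was 1.00 in every case.

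**The case against.** **The loss of participants is inferred.** The SAP does not say that the offset is logged. That is right, so the dropout is conditional on the usual form. Entering ICU days unlogged is no better: expected days would then be multiplied by e for every ICU day, a factor of e^8, about 2,981, between 0 and 8 days.

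**The sizes are invented.** They are illustrative, and a halved ICU stay is a large change. The figures show direction and mechanism, not a forecast. A one-day difference in stay is still enough to move the duration ratio across 1 (1.06 against 0.96).

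**Little hangs on these outcomes.** None of the four is a key secondary endpoint in SAP 7.6. Protocol 10.2 plans to describe secondary hypotheses by summary statistics, and SAP 7.8 makes allowance for multiple testing when results are interpreted. This stands and limits the importance of the point. It does not make the specified estimate right.

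**For new ventilation the offset is less harmful.** Most ventilated participants would plausibly have ICU time, so few may be lost. The ratio would still be ventilated days per ICU day, not the protocol outcome.

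A reader might also infer that ICU time is not collected, since neither schedule of procedures lists it. The documents do not support that: the eCRF is not among them, medical records are source data (Protocol 11.1), and SAP 7.4 refers to linkage with routine clinical data. Nor are the open details on deaths, on participants already on support at baseline, and on the denominators of the two durations of new support consequences of the offset. They are missing detail.

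**Conclusion.** The offset is wrong as written in all four sections and should be corrected. ICU time is neither the protocol's counting window nor fixed at randomisation, and nothing in the documents justifies it.

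The size cannot be known from the documents. Under the stated assumptions, about 80 of 400 participants would enter the free-days models. An ICU stay falling from 8 to 4 days would turn a duration ratio of about 0.86 into about 1.39.

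Two further readings are tempting and do not hold. One is that the models are safe if ICU admission and stay turn out equal between arms; the 0.82 against 0.64 example shows otherwise. The other is that the trial's efficacy conclusion is compromised. The primary ordinal analysis (9.1), incidence of new ventilation (9.2.8), hospital stay (9.2.11) and mortality (9.2.12) do not use this offset. Only these four secondary comparisons are affected.

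**What to change.** 1. In SAP 9.2.6, 9.2.7, 9.2.9 and 9.2.10, delete the clause that makes ICU time the offset.
2. Fit the negative binomial model in the full analysis population over days 1-29 (0-29 for new oxygen). Use no offset, or the log of days observed to day 29 where withdrawal or loss shortens follow-up. SAP 7.7 already covers centre as a random effect.
3. Borrow from 9.2.11 only the absence of an offset. That section is limited to participants discharged alive by day 29, which is itself a selection after randomisation and should not be carried over.
4. State as an explicit assumption that days at home after discharge count as oxygen-free. Supplemental oxygen is not recorded after discharge (Protocol Appendix 4), and categories 1 and 2 of the scale describe activity, not oxygen. The rule in SAP 7.4, "For all participants who were discharged and alive but have missing clinical status, a clinical status scale of 2", therefore does not establish it.

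While the sections are open, it would help to state how deaths and baseline support are handled and who enters the two models for duration of new support.

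Cost: SAP wording and programming only. No new data are needed.

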It is expected that these clinical assessments will be carried out by the clinical team during routine clinical care and documented on a NEWS chart. Where the assessments have been carried out, the results of the assessment closest to 8am on the day will be used to prevent duplication and further exposure of the trial staff to patients with COVID-19.

- Blood pressure and pulse, lying or seated
- Tympanic temperature
- SpO2
- Record if SpO2 has been measured on air or oxygen concentration the participant was receiving.

Ordinal Scale

The ordinal scale is an assessment of the clinical status on a given trial day. Each day, the worst score for that day will be recorded. The scale is as follows:

- 1. Not hospitalised, no limitations on activities
- 2. Not hospitalised, limitation on activities;
- 3. Hospitalised, not requiring supplemental oxygen;
- 4. Hospitalised, requiring supplemental oxygen;
- 5. Hospitalised, on non-invasive ventilation or high flow oxygen devices;
- 6. Hospitalised, on invasive mechanical ventilation or ECMO;
- 7. Death.

NEWS Score

The NEWS score has demonstrated an ability to discriminate patients at risk of poor outcomes. (Smith, 2016). This score is based on 7 clinical parameters. The NEWS2 Score is being used as an efficacy measure.

This should be evaluated at the assessment recorded closest to 8am on a given trial day. These parameters can be obtained from the hospital chart.

Exploratory assessment- viral shedding

Where practical at the Tayside site only, nasal swabs will be obtained on day 15 and day 29 to evaluate viral clearance by PCR.

Exploratory assessment- neutrophil studies

At the Tayside and Sheffield sites only, additional blood will be taken for isolation of peripheral blood neutrophils, as per outcome measures section 3.7.

Exploratory assessment- quality of life

The validated EQ-5D-5L quality of life tool will be administered to patients who are able to complete the questionnaire either in person (those still in hospital) or over the telephone (those at home) to determine the impact of treatment on quality of life.

Clinical Evaluation

As these participants are in-patients receiving care for COVID-19, they will be monitored as per clinical need. Where already obtained for clinical need the following blood results will be recorded at days 1, 3, 5, 8, 11, 15, 29:

- White cell count, haemoglobin, platelets, neutrophils, eosinophils, lymphocytes
- creatinine, eGFR
- AST and ALT

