16.4. Appendix 4 – Schedule of Procedures

	Screeningd	Randomization ^d			Follow-up Assessments	Follow-up assessments	Follow-up Assessments	Unscheduled Assessments
Timeline	Day 0 or 1	Day 1 Up to 24 hours after screening	Daily whilst hospitalised	Days 3, 5 &11 ° (telephone call if at home)	Day 8° (telephone call if at home)	Day 15 ° (telephone call if at home)	Day 29 ^c (telephone call if at home ^b)	As Required in the event of AE
Informed Consent	Х				,			
Inclusion/Exclusion Criteria Check	Х	Х						
Medical History	Х							
Record Concomitant Medications	Х	Х			Х	Х	Х	Х
Check Vital Signs*^	Х	Х			X∞	X∞	X∞	X
ECG*	Х							
Full blood count*+	Х			X∞	Х∞	X∞	X∞	
Urea and electrolytes*+	Х			X∞	X∞	X∞	X∞	
Liver function tests*+	Х			X∞	X∞	X∞	X∞	
SARS CoV-2 PCR*	Χ							
Record SARS CoV-2 PCR results, only if done for clinical reasons				×	X	×	×	
Nasal swab for SARS CoV-2 PCR* (Tayside only)						X∞	Х	
Research Blood Sample * (Tayside and Sheffield only)		X			X∞	X∞	X	Х
Sputum sample for storage if available*+ (Tayside only)		X			X∞	X∞	Х	
Endotracheal aspirate sample for storage if available*+a (Tayside only)					X∞	X∞	X∞	
Clinical status on 7 point scale	Х	Х	Х	Х	Х	Х	Х	Х
NEWS recording*	Х	Х	Х	X∞	X∞	X∞	X∞	

	Screening ^d	Randomization ^d			Follow-up Assessments	Follow-up assessments	Follow-up Assessments	Unscheduled Assessments
Timeline	Day 0 or 1	Day 1 Up to 24 hours after screening	Daily whilst hospitalised	Days 3, 5 &11 ° (telephone call if at home)	Day 8° (telephone call if at home)	Day 15 ^c (telephone call if at home)	Day 29 ° (telephone call if at homeb)	As Required in the event of AE
EQ-5D questionnaire							Х	
Record supplemental oxygen*	Х	Х			X∞	X∞	X∞	Х
Record CT scan results, only if done for clinical reasons	Х	Х	Х	X∞	X∞	X∞	X∞	X∞
Pregnancy Testing (urine or blood) If Applicable	Х							
Record Adverse Events		X	Х	Х	Х	Х	Х	Х
Randomisation		X						
Dispense Trial Drugs		Χ						
Drug Return And Compliance Check							X	

[^] Vital Signs: Blood Pressure, pulse, temperature, oxygen saturation

^{*}indicates procedures that will be performed by the clinical team as part of routine care but results will be recorded and included in the eCRF. If not performed by the clinical team, but clinically indicated, the research team may assist in this being performed but all processes will avoid duplication and exposure to potentially infected participants.

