⁺Excess biological samples that are being taken for clinical reasons may be stored for future use if no longer required for clinical purposes (Tayside only).

^a For those participants who are intubated.

[∞]These assessments will not be completed if the participant has been discharged from hospital.

^b For the Tayside and Sheffield site only, the day 29 assessments will be carried out face-to-face either at a NHS facility or at the participant's home. Home visits will only be carried out if no one in the household has symptoms of COVID-19.

^cResearch blood samples (Tayside and Sheffield only) and, once discharged, assessments may be completed within +/- 1 day

^dScreening and randomisation may occur on the same day if all eligibility criteria are met. Day of first dose of IMP will be considered as day 1 for the calculation of follow up assessments.

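### Read literally, SAP 9.2.6 does not count oxygen-free days at home between telephone contacts, so for the same oxygen course an earlier discharge gives a lower count

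*SAP*

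**What the plan says.** - **Endpoint.** Protocol 3.7 lists "Oxygen free days" under oxygenation, with days 1 to 29 as the time frame.
- **Derivation.** SAP 9.2.6: "Number of days will be calculated as the number of days free from oxygen support reported on the 7-point ordinal scale eCRF". It gives no rule for days without a record. The comparison is a negative binomial regression with time in ICU as the offset.
- **Recording in hospital.** In Protocol Appendix 4 (repeated as SAP Table 1), the row "Clinical status on 7 point scale" is marked in the column "Daily whilst hospitalised".
- **Recording after discharge.** The same row is marked on days 3, 5, 8, 11, 15 and 29, each carried out as a "telephone call if at home" (Tayside and Sheffield see participants in person on day 29). The ±1 day window after discharge moves a contact but does not add one.
- **Span of one record.** Protocol 7.8: "The ordinal scale is an assessment of the clinical status on a given trial day". It does not describe the interval since the last contact.
- **Separate oxygen record.** The supplemental-oxygen row carries the infinity mark on days 8, 15 and 29, whose footnote reads "These assessments will not be completed if the participant has been discharged from hospital".
- **Missing status.** SAP 7.4 assigns category 2 to participants discharged alive whose clinical status is missing. The sentence follows one on day-29 follow-up and does not mention oxygen-free days.

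**The concern.** The window has 29 days, but the named source form holds a record for every day only while the participant is in hospital. Under the literal rule an oxygen-free day on the ward scores 1 and an oxygen-free day at home between contacts scores 0. The count then depends on where the participant was as well as on oxygen use.

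This bears on the treatment comparison because the trial's hypothesis (Protocol 1, SAP 3.1) is that the drug reduces days dependent on oxygen and also shortens hospital stay. The first effect raises the count; the second removes recorded days and lowers it. A real benefit could be largely hidden on this endpoint. The offset does not help, since time in ICU is not the number of days with a record.

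**Working it through.** The documents give no expected value for oxygen-free days, so there is no stated figure to reproduce. The check counts records under the 9.2.6 wording and compares them with the calendar count.

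**Inputs from the documents**
- Window: days 1 to 29 (Protocol 3.7).
- Contact days C = {3, 5, 8, 11, 15, 29}; daily records in hospital (Protocol Appendix 4).

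**Assumed participant profiles**
- f = first oxygen-free day, with the participant alive and off oxygen from then to day 29.
- h = last day with an in-hospital record.

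**Formulas**
- Calendar count = 29 − f + 1.
- Literal count = number of days d from f to 29 with d ≤ h or d in C. A contact day showing category 1 or 2 is taken as oxygen-free.

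**Step 1. Same oxygen course, different discharge day.** Take f = 4, so the calendar count is 29 − 4 + 1 = 26. With h = 5, the counted days are 4 and 5 in hospital and 8, 11, 15 and 29 by contact: 2 + 4 = 6. Other values of h:

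| Last in-hospital record | In hospital | Later contacts | Counted | Lost from 26 |
|---|---|---|---|---|
| day 5 | 2 | 4 | 6 | 20 |
| day 8 | 5 | 3 | 8 | 18 |
| day 12 | 9 | 2 | 11 | 15 |
| day 15 | 12 | 1 | 13 | 13 |
| day 20 | 17 | 1 | 18 | 8 |
| day 29 | 26 | 0 | 26 | 0 |

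**Step 2. Ranking between two participants.** Someone on oxygen to day 14 and then in hospital off oxygen to day 29 has f = 15, h = 29: counted 15, calendar 15. Against the first row above (6 counted, 26 calendar), the order reverses. This pair is a deliberately extreme illustration.

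**Step 3. Effect on a treatment difference (assumed distributions).** Lognormal time on oxygen with median about 6 days; lognormal further hospital stay with median 2.5 days; log-SD 0.8 for both; no deaths; no ICU offset. Control means are 6.25 counted and 20.6 true. The drug is assumed to cut time on oxygen by 25%, a true gain of about +1.8 to +1.9 days.

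| Change in post-oxygen stay | Counted difference (days) |
|---|---|
| none | +0.47 |
| −10% | +0.22 |
| −25% | −0.15 |
| −40% | −0.51 |

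With a median post-oxygen stay of 1 day instead of 2.5, all four differences are positive, from +0.48 down to +0.13. Part-day rounding moves the counted control mean by a few tenths but hardly changes the differences.

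Varying median oxygen time over 5 to 8 days, median post-oxygen stay over 1.5 to 4 days and log-SD over 0.6 to 1.0, with stay unchanged, gave a true gain of +1.5 to +2.3 days and a counted gain of +0.4 to +0.7, under a third of it. With both times cut by 25%, the counted difference ran from negative values to about +0.2.

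**Step 4. After the fix.** If every day alive off oxygen after discharge counts, f = 4 gives 26 for any h, and f = 15 gives 15. The dependence on discharge day disappears.

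**The case against.** The strongest reply is that 9.2.6 names a source form and does not say that an unrecorded day scores zero. SAP 7.4 assigns category 2 to all participants discharged alive with missing status, and that sentence is not expressly confined to day 29. Category 2 lies outside the oxygen categories 4 to 6, so applying it to each unrecorded home day would restore the full count. Admission, discharge and death dates are collected, and SAP 7.4 mentions linkage to routine data, so a programmer could fill the days sensibly.

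This stands as a possible reading, but the SAP does not adopt it. Section 7.4 speaks of missing status, and a day with no scheduled assessment is not obviously missing. Section 9.2.6 counts days that are reported. Categories 1 and 2 describe activity limitation and are silent on oxygen at home. Two programmers could return 6 and 26 for the same participant.

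Other parts of the reply stand in full. Table 2 of the SAP anticipates 38 + 42 = 80% of controls out of hospital, but that is status on a single day and says nothing about discharge timing. Crediting oxygen-free days before death follows the plain wording of the endpoint; a score of zero would be a composite that the protocol does not define. SAP 9.2.9 names no source form for ventilator-free days. Oxygen-free days are one of several oxygenation outcomes and are not among the key secondary endpoints listed in SAP 7.6.

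**Conclusion.** The point holds as a defect in a stated derivation rule. For the same oxygen course, earlier discharge lowers the literal count, by 20 of 26 days in the worked case. That arithmetic needs only the schedule and the wording of 9.2.6; the participant profiles are illustrative.

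Loss of most of a true gain is consistent across the assumed distributions examined. A reader might infer that the endpoint would show harm from an effective drug. The documents do not support that as a general result: reversal needs a sufficient cut in post-oxygen stay as well, and it vanished for the reductions tested when the assumed median stay was 1 day. The documents give no distribution of oxygen days or discharge days, so the size of the actual between-arm bias cannot be computed. If the drug does speed discharge, the bias runs against it.

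This should be fixed before unblinding. It affects a secondary endpoint. The primary day-29 analysis, mortality and the time-to-event analyses do not use this count.

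**What to change.** Replace the counting sentence in SAP 9.2.6 with a definition along these lines: oxygen-free days are the number of days from 1 to 29 on which the participant is alive and not in category 4, 5 or 6; in-hospital days are taken from the daily scale; every day alive from discharge to day 29 counts as oxygen-free unless readmission on oxygen is recorded.

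Add three statements:
- Oxygen used at home is not recorded after discharge, so such days are treated as oxygen-free; this is a limitation.
- How participants who die are scored. This point does not require a score of zero.
- Whether the category-2 rule in SAP 7.4 applies only to scheduled assessments.

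If ventilator-free days (SAP 9.2.9) are derived from the same form, use the same construction with category 6.

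The cost is a short SAP amendment and a few lines of derivation code. Admission, discharge and death dates are already endpoint data, and Protocol 9.3 has records checked for hospitalisations at every contact. No new data collection is needed.
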